11.4.4 Intra-procedural data

Initial cryoablation procedure information including the type of procedure, tumor size, cryoablation needle type and the number of each type of needle used, freeze and thaw times, and how ice formation encompasses the tumor will be summarized.

11.4.5 Other Analyses

Kaplan-Meier, T-Tests and other appropriate statistical tests may be performed on various parameters depending on the data collected during the study.

11.4.6 Poolability Analyses

Though individual treatments may vary (needle used, number of needles used, and freeze/thaw times, etc.), it is expected that data will be poolable across study sites since all sites and investigators will follow a common protocol with identical inclusion/exclusion criteria (same population) and outcome assessment. The primary efficacy endpoint will be evaluated by study site.

12 DATA MANAGEMENT

12.1 Data Collection

Data will be collected using a web-based electronic data capture (EDC) system. The system will be fully validated and compliant with FDA 21 CFR Part 11 Guidance. Participating sites will enter all subject data collected during the conduct of the protocol into the EDC system using the electronic case report forms (eCRFs) developed for each stage of the study.

All sites will receive training on the proper use of the system and the data collection expectations for this protocol. A Galil Medical representative will train each site on how to create a new subject, enter data into the eCRFs, edit/update data on existing eCRFs, resolve queries and approve/sign-off on each form/completed eCRF.

12.2 Data Processing

To help minimize data entry errors, the EDC system will include real-time edit checks that will identify potential data issues at the time of entry. These edit checks will display on-screen messages when triggered so that the investigator or data entry designee can immediately review the potential data issue and address it before leaving the system.

All eCRFs will be reviewed by a Galil Medical representative to check for completeness and potential unresolved data entry issues. A Galil Medical representative will generate queries within the system for open data issues and follow-up with each site, as necessary, to resolve key data element issues.

The investigator will review all eCRFs entered and will approve each eCRF for a subject via electronic signature within the EDC system. The database will be subject to periodic interim analyses based on key study milestones (e.g. adverse event assessments and primary endpoint after completed by all participating subjects). Prior to each milestone analysis, a Galil Medical representative will work with each site to ensure a data set that is as complete and accurate as possible. At the conclusion of the study, the database will undergo a final review and then be locked. No changes will be allowed in the database after the final lock without the written authorization of the appropriate Galil Medical management team members.

13 MONITORING AND AUDITING PROCEDURES

Participating sites will be managed remotely via regular telephone/email contact and routine monitoring visits will be conducted. When necessary, site visits will be performed by an authorized representative from Galil Medical, and will be conducted according to the monitoring plan and applicable FDA and GCP guidelines.

In addition, sites may be subject to an audit visit by Galil Medical, the FDA or a local regulatory authority. If such a site audit occurs, the investigator agrees to provide access to all pertinent subject records, eCRFs and other site documents deemed necessary to complete the audit visit.

By signing the Study Agreement, the investigator grants permission to authorized representatives of Galil Medical to conduct on-site monitoring visits for the purpose of reviewing the collected study data and to review site procedures employed in the conduct of this study.

It is important that the investigator(s) and their relevant personnel are available during the monitoring visits and possible audits or inspections and that sufficient time is devoted to the process.

14 SAFETY ASSESSMENTS

All related, potentially related, or unknown to be related adverse events (AEs), serious adverse events (SAEs) and unanticipated adverse device effects (UADEs) that occur within 30 days after the cryoablation procedure is performed will be recorded. A related event is one in which the investigator determines there is a reasonable possibility that the procedure/study device caused or contributed to an adverse event. The AEs, SAEs and UADEs identified will be followed until resolution or for a period of 6 months.

14.1 List of Definitions.

Adverse Event (AE)

An adverse event is defined as any untoward or unfavorable medical occurrence in a human subject, including any abnormal sign (for example, abnormal physical exam or laboratory finding), symptom, or disease, temporally associated with the subject's participation in the research, whether or not considered related to the subject's participation in the research. According to this protocol, only those related, potentially related, or unknown to be related (to the cryoablation procedure) adverse events will be collected. Adverse events which are related to a pre-existing condition or treatment of that condition (noted in subject records as existing prior to the cryoablation procedure) will not be documented as adverse events. All AEs (as specified above) must be recorded in the electronic database. A description of the event, including the start date, resolution date, action taken and the outcome should be provided, along with the investigator's assessment of the relationship between the AE and the study procedures.

The anticipated cryoablation related adverse events and their corresponding Common Terminology Criteria for Adverse Events (CTCAE) Terms are listed in Appendix B.

Serious Adverse Event (SAE)

Category 4 or higher of the CTCAE guidelines and/or the following ICH definitions will be used in the protocol as applicable. According to this protocol, only those related, potentially related, or unknown to be related (to the cryoablation procedure) serious adverse events will be collected.

- Results in Death
- Is Life-threatening

Note: the term 'life threatening' in the definition of serious refers to an event in which a subject was at immediate risk of death at the time of the event; it does not refer to an event which hypothetically might have caused death if it were more severe.

- Requires inpatient hospitalization or prolonged existing hospitalization

Note: complications that occur during hospitalization are AEs. If a complication prolongs hospitalization or fulfills any other serious criteria, the event is serious. Hospitalization for elective treatment of a preexisting condition that did not worsen from baseline is not considered to be an AE.

- Results in persistent or significant disability/incapacity

Note: the term disability means a substantial disruption of a person's ability to conduct normal life functions. This definition is not intended to include experiences of relatively minor medical significance (e.g., uncomplicated headache, nausea, vomiting, diarrhea, influenza, or accidental trauma) that may interfere or prevent everyday life functions, but do not constitute a substantial disruption.

- Results in permanent impairment of a body structure or body function or requires surgical intervention to prevent permanent impairment of a body structure or body function
- Leads to fetal distress, fetal death or a congenital anomaly/birth defect
- Important medical events that may not be immediately life threatening, or result in death or hospitalization but may jeopardize the subject or may require intervention to prevent one of the outcomes listed in the definition above should also usually be considered serious

Note: Examples of such events are intensive treatment in an emergency room or at home for allergic bronchospasm, blood dyscrasias, or convulsions that do not result in hospitalization; or development of drug dependency or drug abuse.

Unanticipated Adverse Device Effect (UADE)

Unanticipated adverse device effect is any serious adverse effect on health or safety, any life-threatening problem or death caused by, or associated with a device, if that effect, problem, or death was not previously identified in nature, severity, or degree of incidence in the application; or any other unanticipated serious problem associated with a device that relates to the rights, safety, or welfare of subjects.

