6.4 Risks

Potential risks of bone tumor cryoablation in the intraoperative/early postoperative period include bleeding, infection, fracture, nerve injury, skin injury (burn/frostbite) and injury to adjacent tissues or organs.

Potential delayed risks of cryoablation include complications that may lead to death. A list of anticipated adverse events may be found under Appendix B. There may be unforeseen complications, and other complications may occur in the location of the tumor treated by cryoablation.

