14.3 Recording Related AEs

All related, potentially related, or unknown to be related adverse events must be recorded on the eCRF. The investigator will review all documentation (e.g., hospital progress notes, laboratory, or diagnostic reports) relative to the event and record all relevant information regarding an AE in the eCRF.

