14.4 Recording and Reporting Related SAEs and UADEs

Any related, potentially related, or unknown to be related serious adverse events must be reported by the investigator within **24 hours** of learning of the event. The site must maintain adequate documentation of timely event reporting.

Reporting of SAEs and UADEs may be done via telephone at [REDACTED] or via E-mail at [REDACTED]

A Galil Medical clinical representative will work with the investigator to complete the SAE report. The investigator or designee must forward the requested follow-up information to the Galil Medical clinical representative as the event continues and/or resolves.

Investigators are required to submit to the Institutional Review Board (IRB)/Independent Ethics Committee (IEC) and Galil Medical a report of any UADE occurring during an investigation as soon as possible, but in no event later than 10 working days after the investigator learns of the effect. The site must maintain adequate documentation of timely event reporting.

Delegated study personnel are to enter the SAE/UADE information into the eCRF EDC system. It is the responsibility of the investigator to inform the IRB/IEC of SAEs/UADEs as required by local procedure. Galil Medical is responsible for relaying adequate information on SAEs/UADEs to all investigators participating in this study as well as to the FDA and other regulatory authorities.

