16.3 Institutional Review Board/Independent Ethics Committee

This protocol, the Informed Consent Form (ICF) and relevant supporting information must be submitted to an Institutional Review Board / Independent Ethics Committee (IRB/IEC) before a site is initiated for participation. Approval from the IRB/IEC must be obtained before any study assessments are performed. IRB/IEC approval shall be documented in a letter to the investigator, clearly identifying this protocol, the documents reviewed and the date of approval. This protocol will be conducted in accordance with applicable local regulatory and IRB/IEC requirements.

The investigator is responsible for keeping his/her local IRB/IEC apprised of the progress of the study and of any protocol changes, as necessary. Galil Medical will be responsible for updating the study's central IRB/IEC, if applicable.

Investigators are required to notify their local IRB/IEC of all Serious Adverse Events (SAEs) and all Unexpected Adverse Device Events (UADEs). Investigators under the jurisdiction of the study's central IRB/IEC are required to promptly notify Galil Medical of such events so that they can notify the central IRB/IEC.

The investigator will be responsible for obtaining annual IRB/IEC approval and renewal throughout the duration of the study.

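### Section 14 records only events with onset by day 30, section 14.4 requires any UADE during the study to be reported and entered, and the safety analysis states no onset period

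*Protocol*

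**What the plan says.** - **Protocol section 14, opening paragraph.** Adverse events, SAEs and UADEs that are related, possibly related or of unknown relation are kept if they are ones "that occur within 30 days after the cryoablation procedure is performed will be recorded". Once identified, they "will be followed until resolution or for a period of 6 months". The first statement is a limit on onset. The second is a length of follow-up.
- **Protocol 14.3.** "All related, potentially related, or unknown to be related adverse events must be recorded on the eCRF". No onset limit is given.
- **Protocol 14.4, SAEs.** The duty begins "Any related, potentially related, or unknown to be related serious adverse events must be reported by the investigator within"; the limit then given, one day from awareness, is a reporting deadline, and no onset limit is given.
- **Protocol 14.4, UADEs.** Investigators must submit "a report of any UADE occurring during an investigation as soon as possible", and no later than 10 working days after learning of it. The period named is the investigation.
- **Protocol 14.4, data entry.** "Delegated study personnel are to enter the SAE/UADE information into the eCRF EDC system".
- **Protocol 16.3.** Investigators notify the IRB/IEC of all SAEs and UADEs. No onset limit is given.
- **Protocol 5.2 and 11.4.3, and the SAP under Safety Endpoint Analysis.** These call for incidence and severity, with point estimates and two-sided exact 95% confidence intervals in four event categories. None states a period.
- **Protocol Table 1 and 8.5.** A safety assessment is scheduled at every follow-up visit from week 1 to week 24.

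**The concern.** An incidence needs a stated period. Here the only period is in a recording rule, and a reporting rule in the same section names a different one for UADEs. Two consequences follow.

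First, a UADE after day 30 can reach the database through 14.4 while lying outside the opening paragraph's limit. The analyst then has to decide, after seeing the data, whether it enters the UADE estimate.

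Second, if the 30-day rule is applied as written, a related non-serious event starting after day 30 is never recorded, even if a subject reports it at a scheduled safety assessment. No later analysis can recover it.

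Protocol 3.3 says the data are meant to support a labelling expansion, so a reader of the safety table needs to know which period it covers.

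**Working it through.** The plan gives no figure for this point, so there is nothing to reproduce. The check is a comparison of rules.

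**Step 1: apply each rule to one case.** Take an event judged related, with onset on day 60, in a subject still in follow-up. The study runs to week 24 (24 × 7 = day 168), so day 60 is within the investigation.

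| Event, onset day 60 | Section 14 opening | 14.3 or 14.4 | 16.3 | In the exact intervals? |
|---|---|---|---|---|
| Non-serious related AE | Not recorded | 14.3 sets no limit but may inherit 30 days | Does not apply | Not stated; lost if not recorded |
| Related SAE, not a UADE | Not recorded | 14.4 SAE sentence sets no limit but may inherit 30 days | Notify IRB/IEC | Not stated |
| UADE | Not recorded | 14.4 names the investigation as the period: report and enter in EDC | Notify IRB/IEC | Not stated |

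Only the UADE row contains two express rules that disagree. In the other rows, 14.3 and the SAE sentence of 14.4 are silent on onset.

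**Step 2: check whether safety contacts exist after day 30.** From Table 1, a visit window is week × 7 days, ±5 days at week 1 and ±12 days at the others.

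- Week 4: 28 ± 12 = days 16–40, which straddles day 30.
- Week 8: 56 ± 12 = days 44–68, wholly after day 30.
- Weeks 12, 16, 20 and 24 are later still; the last is 168 ± 12 = days 156–180.

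The visits at which a later event could be picked up therefore already exist. This shows only that capture is feasible. It does not measure the conflict.

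**Step 3: see what one event does to an estimate.** Assume a denominator of 60, the planned number treated (protocol 11.2). The safety analysis uses the per-protocol population, whose size is not given; a smaller denominator would widen each interval. The limits are two-sided exact (Clopper–Pearson).

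- 0/60: 0%, upper limit 1 − 0.025^(1/60) = 6.0%.
- 1/60: 1.7%, interval 0.04% to 8.9%. The lower limit is 1 − 0.975^(1/60).
- 2/60: 3.3%, interval 0.4% to 11.5%.

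This is an illustration, not a forecast. In a category with few events, whether a single late event counts changes what is reported.

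**Step 4: number of events affected.** This would need a distribution of onset times for related events. The documents give none, so it cannot be computed.

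**The case against.** The strongest reply is that silence is not contradiction. The opening paragraph of section 14 sets the scope for AEs, SAEs and UADEs together. Section 14.3 and the SAE sentence of 14.4 reuse its relatedness filter and offer no rival window, and 14.1 refers back to scope already specified. On this reading the 30-day limit carries through, and the analysis covers 30 days because only 30 days are recorded. A 30-day window for related events is also a legitimate design choice. Site training and sponsor review of every eCRF would reduce divergent readings.

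Much of this stands. A reader might infer that 14.3, 14.4 and 16.3 all contradict the opening paragraph. The documents do not support that: 14.3 and the SAE sentence can inherit the limit, and 16.3 concerns IRB/IEC notification, not the study dataset. A reader might also take the later safety assessments as proof of conflict, but they can serve the 6-month follow-up of earlier events. Section 6.4 says "Potential delayed risks of cryoablation include complications that may lead to death", but gives no day, so it does not show that onset after day 30 is expected.

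The reply does not dispose of the UADE sentence in 14.4, which names its own period and is tied to EDC entry. Nor does it supply a period for the analysis: if late UADEs are entered under 14.4, the recorded data are not confined to 30 days.

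**Conclusion.** The point holds in limited form. The opening paragraph of section 14 and the UADE rule in 14.4 cannot both govern a UADE with onset after day 30, and neither document says which period the safety estimates cover. Applied as written, the opening paragraph also leaves later related non-serious events unrecorded while safety assessments continue to week 24.

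The size in events is unknown. A reader might conclude that incidence will be understated. That follows only if the estimates are read as covering the full 24 weeks, and no section states that target. As an estimate of 30-day incidence, a consistently applied 30-day rule would not be understated for that reason.

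The conclusion rests on the wording alone and assumes no rate of late events. It should be fixed, because an event that was never recorded cannot be added at analysis.

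**What to change.** Reconcile the opening paragraph of section 14 with 14.3, 14.4 and 16.3 so that one onset window governs recording and analysis. State that window in protocol 11.4.3 and in the SAP's safety section.

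The simplest option is to record related events from the procedure to week 24 or study exit. The visits, eCRF and relatedness filter are already in place, and 14.2 already collects onset date. Report incidence for days 0–30, which keeps the 30-day figure, and separately for onset after day 30. For the later period, give the number of subjects still followed at day 31 and the losses to death and dropout. This matters because protocol 11.2 expects 30% attrition by week 8, or 0.30 × 60 = 18 of the planned subjects.

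If the sponsor keeps 30 days, the analysis sections should say so, and should say how a later UADE entered under 14.4 will be presented.

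The cost is a short protocol amendment, a matching SAP revision and some additional adverse-event entries, the number of which is unknown. No new visit or data field is needed.

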Tissue thermal sensors may be employed to enable the real-time tissue temperature monitoring, thus, contributing to the safety and effectiveness of the procedure.

Cryoablation procedures using Galil Medical's systems may be performed under the guidance of Ultrasound (US), Computed Tomography (CT) or Magnetic Resonance Imaging (MRI).

1.2. *Historical Background of Bone Metastases and Standard Treatments*

It is estimated that more than 1.6 million new cases of cancer will be diagnosed in 2015 in the United States. Prostate cancer is the most common cancer among men (26%), followed by lung (14%) and colon & rectum (8%) cancers. Up to 85% of patients with these primary cancers have evidence of metastasis to the bone at the time of death.^{21,22} As the tumor invades the bone tissue, this creates holes that make the bone thin and weak, and nerve endings in and around the bone send pain signals to the brain. Bone metastases frequently result in pain, pathologic fractures, hypercalcemia, and spinal cord compression. Pain symptoms are typically intermittent, but can be sharp and severe. Pain may be partially eased by activity, and is commonly worse at night. Metastases to the bone are best identified with imaging, most commonly radiography (X-rays) and scintigraphy (bone scans), and occasionally MRI.²³

The standard of care for patients with bone metastases is mainly palliative and consists of local therapy (radiation, also called radiotherapy, and surgery), systemic therapy (chemotherapy and hormone therapy), and analgesics. Unfortunately, metastatic bone disease often does not respond to chemotherapy or hormonal therapy and surgery may not be an option for those patients with advanced disease or poor overall health.²²

External beam radiation has been proven to provide good pain relief for some patients. In their Cochrane review, McQuay et al. concluded that radiation therapy is clearly effective at reducing pain from painful bone metastases. A review of twenty trials reported on 43 different radiation fractionation schedules and eight studies of radioisotopes in which radiation produced complete pain relief at one month in 395/1580 (25%) patients, and at least 50% relief in 788/1933 (41%) patients at some time during the trials.²⁴

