3.2 Previous Clinical Studies Leading Up to and Supporting the Proposed Research

Ullrich et al. reported a series of 4 patients treated with cryoablation for palliation of metastatic bone pain. Three of the four patients reported significant improvement in pain immediately after treatment. The fourth patient experienced more pain due to an insufficiency fracture which resulted because the tumor was not amenable to post-procedure enforcement.³⁵

Sewell et al. reported the use of MRI guided cryoablation for bone tumors in 2002. A series of 16 tumors were treated in patients using the Galil CryoHit System. Mild procedural pain associated with probe placement was reported. Immediate postoperative reduction in pain was documented. No immediate or long term complications were reported. Early results demonstrated continued pain relief and significant increase on the patient's quality of life.⁴¹

Callstrom et al. evaluated the safety and effectiveness of percutaneous cryoablation in series of 14 patients with metastatic bone tumors for the reduction of pain. Patients were included in the study if they presented with one or two painful metastatic tumors, had a score of 4 or greater out of 10 for worst pain in 24 hours, and did not respond to or refused radiation or chemotherapy. The CT guided percutaneous cryoablation was performed with one or more cryoprobes (Endocare; Perc-17, Perc-22, and Perc-24). A single probe was used for tumors <3cm and 2-7 probes were used in larger tumors. A 10 minute freeze, 8 minute thaw, and a 10 minute freeze followed by a final thaw was intended, however treatment times ultimately varied due to coverage and proximity of adjacent structures. All tumors involved bone with osteolytic bone destruction or periosteal reaction and a soft tissue mass. Tumors ranged in size from 1-11 cm in diameter. The mean cryoablation procedure time was 139 minutes \pm 53. The mean time required in the CT suite was 185 minutes \pm 56. No major complications were reported with the

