14.2 Causality Assessment

The investigator's assessment of causality must be provided for all adverse events (serious and non-serious). An investigator's causality assessment is the determination of whether there exists a reasonable possibility that the procedure or study device caused or contributed to an adverse event. If the investigator's final determination of causality is unknown and the investigator does not know whether or not the procedure or study device caused the event, then the event will be handled as "related to procedure or study device" for reporting purposes. If the investigator's causality assessment is "unknown but not related to procedure or study device," this should be clearly documented on study records.

The investigator will evaluate AEs/SAEs/UADEs using the following guidelines:

- Description of event (if the event consists of multiple signs and symptoms, a diagnosis should be recorded rather than each sign and symptom)
 - Record term and grade according to the CTCAE 4.03 grading criteria
- Onset date
- Stop date (if available)
- Seriousness
 - The investigator must determine whether or not the AE meets the definition of serious as noted above. If the event is serious, the investigator must inform the Sponsor within 24 hours of knowledge of the event.
- Relationship to Study Procedure or Study Device
 - The investigator must make a causality assessment for all AEs and decide whether there is a reasonable possibility the AE was caused by the procedure or study device.
 - If there is a valid reason to suspect a causal relationship between the AE and the procedure or study device, the AE should be considered "related or possibly related" to the procedure or study device.
- Outcome
- Action Taken

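### The pre-existing-condition exclusion in Protocol 14.1 conflicts with the duty to record possibly related events, so index-site tumor pain and fracture could go unrecorded

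*Protocol*

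**What the plan says.** Two rules in the protocol's safety section decide whether an event is recorded.

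- **Recording rule.** Section 14 requires recording of related, potentially related and unknown-relation events within 30 days of the procedure. An event is related when the investigator judges that "there is a reasonable possibility that the procedure/study device caused or contributed to an adverse event". Section 14.1 repeats that "only those related, potentially related, or unknown to be related (to the cryoablation procedure) adverse events will be collected". Section 14.2 handles an event as related for reporting when causality is unknown and "the investigator does not know whether or not the procedure or study device caused the event". Section 14.3 requires all of these on the eCRF.
- **Exclusion rule.** Later in the same 14.1 paragraph, a sentence begins "Adverse events which are related to a pre-existing condition or treatment of that condition" and, after an opening bracket, continues "noted in subject records as existing prior to the cryoablation procedure) will not be documented as adverse events".

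The pre-existing condition is universal here: inclusion criterion 7.2.5 requires pain from a metastatic lesion involving bone. Section 1.2 says of that condition: "Bone metastases frequently result in pain, pathologic fractures, hypercalcemia, and spinal cord compression". Appendix B, which 14.1 presents as the anticipated cryoablation-related events, lists both tumor pain and fracture. Section 6.4 says the early procedural risks "include bleeding, infection, fracture, nerve injury, skin injury (burn/frostbite) and injury to adjacent tissues or organs"; it names fracture but not tumor pain.

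Protocol 11.4.3 and the SAP's Safety Endpoint Analysis report point estimates with exact 95% intervals for procedure-related events in the per-protocol population, without hypothesis tests.

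**The concern.** The local harms most relevant to the device, a pain flare at the treated lesion and a fracture through treated bone, are also what the underlying metastasis produces. An investigator can therefore truthfully call such an event related to the pre-existing condition and, under the exclusion, not document it, even where the procedure may have contributed.

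Joint causation is realistic. Section 3.2 describes a small cryoablation series in which "The fourth patient experienced more pain due to an insufficiency fracture", and attributes the fracture to a tumor that could not be reinforced after the procedure. Under 14.1 as worded, one site could record that event and another could omit it.

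The safety endpoint is the incidence and severity of procedure- or device-related events, in a study meant to support a labelling expansion (section 3.3). There is no control arm to reveal an excess, follow-up imaging is discretionary (9.7), and the follow-up list in 8.5 does not name fracture outside the general safety assessment. The Medical Monitor (section 17) reviews the safety data and would not see in them an event that was never entered.

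**Working it through.** No figure in the plan depends on the exclusion, so there is nothing to reproduce. The check is a comparison of the texts, followed by an illustration with assumed counts.

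**Step 1: apply both rules to an event at the index site.**

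| Cause, as judged by the investigator | Recording rule (14 to 14.3) | Exclusion (14.1) | Result |
|---|---|---|---|
| Metastasis only | Not collected | Not documented | Rules agree; outside the endpoint |
| Procedure only | Collected | Does not apply | Rules agree |
| Metastasis, with a possible procedure contribution | Collected, since contribution suffices | Not documented, since it is related to the metastasis | Conflict |
| Unknown | Collected, handled as related | Depends on whether the site first labels it as disease | Unclear |

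**Step 2: look for a tie-break.** There is none. The exclusion follows the recording rule within 14.1 and precedes the instruction that all AEs, as specified above, be recorded, so a site can read it as narrowing that duty. The causality steps in 14.2 apply to adverse events; one screened out at the definition need not reach them. A qualifier about not worsening from baseline does appear in the hospitalization note of the SAE definition, but not in the AE definition.

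**Step 3: direction.** Omission removes events from the numerator and leaves the denominator unchanged, so any bias is downward. It arises only for the third and fourth rows of the table.

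**Step 4: illustration.** Inputs:

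- n = 60 treated subjects (Protocol 11.2), an upper limit, because the safety analysis uses the per-protocol set, whose size is not stated.
- n = 42 (the evaluable target), as an assumed smaller set.
- Assumed: 6 procedure-contributed index-site events, each in a different subject, which full assessment would rate related, possibly related or unknown.

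Exact (Clopper-Pearson) 95% intervals:

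| Events recorded | n = 60 | n = 42 |
|---|---|---|
| 6 (none omitted) | 10.0% (3.8 to 20.5) | 14.3% (5.4 to 28.5) |
| 3 (half omitted) | 5.0% (1.0 to 13.9) | 7.1% (1.5 to 19.5) |
| 0 (all omitted) | 0% (0 to 6.0) | 0% (0 to 8.4) |

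In expectation, with true rate p and omitted share q, the recorded rate is p(1 − q), and the chance of recording no event in 60 subjects is (1 − p(1 − q))^60. With q = 0.5:

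- p = 5%: recorded rate 2.5%; chance of no recorded event rises from 0.95^60 = 4.6% to 0.975^60 = 21.9%.
- p = 10%: recorded rate 5.0%; the chance rises from 0.2% to 4.6%.
- p = 15%: recorded rate 7.5%; the chance rises from below 0.1% to 0.9%.

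With q = 0 nothing changes; with q = 1 the recorded rate is zero. The documents give neither p nor q.

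**The case against.** The strongest reply is that the protocol already requires jointly caused events to be recorded. Contribution is enough for relatedness, potentially related and unknown events are collected, and Appendix B tells investigators to expect tumor pain and fracture. Read as a whole, section 14 points toward recording. The SAE definition has its own collection sentence and does not repeat the exclusion, so a fracture needing admission or surgery, if potentially related, falls under the 24-hour reporting duty in 14.4. All of this stands, and it is why the events could, not would, be lost. It does not settle which rule governs a non-serious event that meets both.

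Three stronger inferences are tempting and not supported:

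- *That the safety rates are biased low.* The endpoint is procedure-related events, so omitting pain or fracture due only to disease is not bias. Bias needs events with a procedure contribution and sites that apply the exclusion first; the documents show neither how many nor how often.
- *That the study cryoablation is itself treatment of the pre-existing condition, so its complications are all excluded.* The bracketed words about what the records show before the procedure count against this, and the reading would empty section 14 and Appendix B. It is strained, though one sentence would close it off.
- *That an omitted event is beyond recovery.* The BPI is completed at baseline and at all seven follow-up visits, further therapies to the index tumor are collected, and source records are retained and open to monitoring. A flare present at a visit would show in the BPI, though not in the AE rates. For fracture the gap is wider.

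**Conclusion.** The conflict is real and more than a missing detail: a categorical exclusion sits beside a recording rule that reaches some of the same events, every subject has the condition that triggers it, and no precedence is stated. Index-site tumor pain (Appendix B) and fracture (Appendix B and section 6.4) could go unrecorded at sites that apply the exclusion first.

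Only the direction of any bias can be concluded. The tables above rest on assumed counts, rates and omitted shares, and on the omitted events being ones that full assessment would rate related, possibly related or unknown. A reader might infer from them that a true 10% would be reported as 5% or 0%; the documents do not support that, and events rated as due only to the metastasis would stay outside the reported rates under any wording. The primary pain analysis does not depend on this rule.

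**What to change.** Amend Protocol 14.1 as follows:

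1. State that the related/potentially related/unknown rule prevails over the pre-existing-condition exclusion.
2. Limit the exclusion to pre-existing conditions that did not worsen from baseline, the qualifier already in the hospitalization note, and to which the procedure did not contribute.
3. Record any fracture, or new or worsened pain, at the index site within the existing event window, with causality as a separate field so that the Medical Monitor can review the attribution. This widens collection slightly, for the index site only.
4. State that only events rated related, possibly related or unknown count in the rates of Protocol 11.4.3 and the SAP's Safety Endpoint Analysis, so the endpoint is unchanged.
5. Clarify that treatment of the pre-existing condition does not include the study cryoablation.

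The cost is a short wording change, a few more AE forms, and a possibly slightly higher reported event rate.
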